TITLE PAGE

Division: Global Medical, Pharma R&D **Information Type:** Epidemiology Study Protocol

Title:	Zanamivir 10 mg/ml solution for infusion pregnancy registry: an observational study of the safety of zanamivir 10 mg/ml solution for infusion exposure in pregnant women with complicated influenza and their offspring.		
Compound Number:	GR121167		
Development Phase	Phase IV		
Effective Date:	23-JUN-2020		
Subject:	Safety of zanamivir	10 mg/mL solution for	infusion in pregnancy
Author(s):	PPD PPD	(GSK), PPD	(GSK),

Copyright 2020 the GlaxoSmithKline group of companies. All rights reserved. Unauthorised copying or use of this information is prohibited

PASS information

Title	Zanamivir 10 mg/ml solution for infusion pregnancy registry: an observational study of the safety of zanamivir 10 mg/ml solution for infusion exposure in pregnant women with complicated influenza and their	
	offspring.	
Protocol version identifier	D-2017N341239_00	
Date of last version of protocol	Not applicable	
EU PAS (ENCEPP) register number	Study to be registered	
Active substance	Zanamivir	
Medicinal product	Zanamivir 10 mg/mL solution for infusion	
Product reference	EMEA/H/C/4102	
Procedure number	Not applicable	
Marketing	GlaxoSmithKline Trading Services Ltd	
authorisation holder(s)	[name]	
	[name]	
	Ireland	
Joint PASS	No	
Research question and objectives	To evaluate pregnancy outcomes among women with complicated influenza exposed to zanamivir 10 mg/mL solution for infusion at any time during pregnancy including: 1) maternal death, 2) pregnancy outcomes including spontaneous losses in clinically recognised pregnancies, induced abortions, stillbirths and live births and 3) birth outcomes including low birth weight, small for gestational age, prematurity, congenital malformations and neonatal death.	
Country(-ies) of study	Member states of the European Union, United Kingdom, Norway and Iceland	
Author	PPD (GSK), PPD (GSK),	

MARKETING AUTHORISATION HOLDER(S)

Marketing authorisation holder(s)	GlaxoSmithKline Trading Services Ltd [name]
MAH contact person	PPD

TABLE OF CONTENTS

PAGE

TIT	LE PAG	Ε	1
1.	LIST O	F ABBREVIATIONS	. 10
2.	RESPC 2.1. 2.2. 2.3. 2.4.	DNSIBLE PARTIES Main Author(s) of the Protocol Principal Investigator Coordinating Investigator(s) Advisory Committee	. 12 . 12 . 12 . 12 . 12 . 12
3.	ABSTR	ACT	.13
4.	AMEN	OMENTS AND UPDATES	.16
5.	MILES	TONES	. 16

1. LIST OF ABBREVIATIONS

AE	Adverse Event	
CDC	Centers for Disease Control	
CEDD	Corrected Estimated Date of Delivery	
CFR	Code of Federal Regulations	
CRO	Contract Research Organization	
CUP	Compassionate Use Program	
EC	Ethics Committee	
eCRF	Electronic Case Report Form	
EDC	Electronic Data Capture	
EDD	Estimated Date of Delivery	
EMA	European Medicines Agency	
EU	European Union	
EU PASS	European Union Post Authorization Safety Study	
EUROCAT	European Registry of Congenital Malformation and	
	Twin Registries	
GPP	Good Pharmacoepidemiology Practice	
GSK	GlaxoSmithKline	
НСР	HealthCare Provider	
HDU	High Dependency Unit	
IAB	Induced Abortion	
ICH	International Council for Harmonisation of Technical	
	Requirements for Pharmaceuticals for Human Use	
ICU	Intensive Care Unit	
IHD	Individual Human Data	
INOSS	International Obstetric Surveillance System	
IRM	Individual Rights Management	
IV	Intravenous	
LBW	Low birthweight	
LMP	Last Menstrual Period	
MACDP	Metropolitan Atlanta Congenital Defect Program	
MCMs	Major Congenital Malformations	
NAI	Neuraminidase Inhibitors	
OXON	Oxon Epidemiology	
REVA-SRLF	REseau de recherche en Ventilation Artificielle – Societe	
	Reanimation de Langue Francaise	
SAB	Spontaneous Abortion	
SAC	Scientific Advisory Committee	
SAP	Statistical Analysis Plan	

SGA	Small for Gestational Age	
SOP	Standard Operating Procedure	
STD	Standard	
sPVP	Study Specific PharmacoVigilance Plan	
STROBE	STrengthening the Reporting of OBservational studies in	
	Epidemiology	
UK	United Kingdom	
UKOSS	United Kingdom Obstetric Surveillance System	

Trademark Information

Trademarks of the GlaxoSmithKline group of companies	Trademarks of non GlaxoSmithKline group of companies
DECTOVA	PASS

2. **RESPONSIBLE PARTIES**

2.4. Advisory Committee

The Scientific Advisory Committee will be convened to provide an independent review of registry data and will include specialists from appropriate fields such as obstetrics, paediatrics, infectious diseases, clinical research, genetics, epidemiology, and teratology from academic institutions, private practice, and/or government agencies.

The composition of the Advisory Committee remains to be determined.

3. ABSTRACT

Title

Zanamivir 10 mg/ml solution for infusion pregnancy registry: an observational study of the safety of zanamivir 10 mg/ml solution for infusion exposure in pregnant women with complicated influenza and their offspring.

Rationale and Background

Pregnant women are a group at risk of increased influenza related morbidity and mortality.

GlaxoSmithKline (GSK) has been awarded a marketing authorisation for zanamivir 10 mg/mL solution for infusion (hereafter referred to as intravenous (IV) zanamivir) under exceptional circumstances, pursuant to article 14 (8) of Regulation (EC) no 726/2004. The indication is:

Dectova is indicated for the treatment of complicated and potentially life-threatening influenza A or B virus infection in adult and paediatric patients (aged ≥ 6 months) when:

- The patient's influenza virus is known or suspected to be resistant to antiinfluenza medicinal products other than zanamivir, and/or
- Other anti-viral medicinal products for treatment of influenza, including inhaled zanamivir, are not suitable for the individual patient.

Dectova should be used in accordance with official guidance.

This prospective observational study aims to evaluate pregnancy outcomes among women exposed to IV zanamivir during pregnancy.

Research Question and Objectives

The objective of the pregnancy registry is to evaluate pregnancy outcomes among women exposed to IV zanamivir at any time during pregnancy. Outcomes of interest will include: 1) maternal death, 2) pregnancy outcomes including spontaneous losses in clinically recognised pregnancies, induced abortions (IABs), stillbirths and live births and 3) birth outcomes including low birth weight (LBW), small for gestational age (SGA), prematurity, congenital malformations and neonatal death.

This registry is primarily descriptive and designed to detect potential safety signals rather than test hypotheses.

Study Design

This pregnancy registry will be a multi-centre, prospective observational cohort study using the United Kingdom Obstetric Surveillance System (UKOSS) and International Obstetric Surveillance System (INOSS) as the principal sources to identify IV zanamivir exposed pregnancies. The registry will collect data directly from healthcare providers (HCPs) based on information that is routinely documented in the participant's medical record as part of usual clinical care. Data will be collected at enrolment as close as possible to the time of exposure to IV zanamivir in pregnancy and at pregnancy outcome (delivery or early termination) with follow up out to three months after delivery to increase birth outcome ascertainment in the infant.

Population

Pregnant women with complicated influenza who have been exposed to at least one dose of IV zanamivir during pregnancy will be eligible to participate in the registry. Minimum criteria for enrolment will be the following:

- Sufficient evidence to confirm exposure to IV zanamivir during pregnancy based on information from the reporter.
- Sufficient information to determine whether the pregnancy is prospectively or retrospectively recorded (i.e., whether the outcome of pregnancy was known at the time of enrolment).
- Date of enrolment into the pregnancy registry.
- Treating hospital contact information to allow for follow-up.
- Women aged >18 years at time of enrolment.

Identification largely via the UKOSS and INOSS systems is proposed, followed by enrolment study staff. De-identified data provided by HCPs under the waiver of informed consent provision will also be collected where allowed under local country laws.

Variables

The exposure of interest will be IV zanamivir during pregnancy.

Outcomes of interest will include: 1) maternal death, 2) pregnancy outcomes including spontaneous losses in clinically recognised pregnancies, induced abortions, stillbirths and live births and 3) birth outcomes including low birth weight, small for gestational age, prematurity, congenital malformations and neonatal death.

Covariates of interest will include: maternal age and ethnicity; prenatal data including estimated date of delivery (EDD); prenatal tests, obstetric history, current pregnancy complications, clinical details of influenza episode, other co-morbidities, concomitant medication exposure and smoking use during pregnancy as well as infant gender and multiple gestations.

Data Sources

Appropriate members of the women's health care team will serve as data reporters to the registry based on information in the medical record. Only data noted as part of routine care will be collected. The registry will perform targeted follow-up to collect additional data on events and outcomes of interest as needed. Congenital malformations will be reviewed by a clinical genetics/teratology specialist on the Scientific Advisory Committee overseeing interpretation of data from the registry.

Study Size

For a range of pregnancy outcomes of interest, sample size calculations considered the number of live births needed to detect the associated effect sizes using a binomial distribution with 80% power and a 1-sided Type I (false positive) error rate of 5%. Assuming prevalence values in the reference population of 2% (major malformations) and 7.6% (preterm births), 100 exposed live births will be sufficient to detect a 4-fold increase in the risk of major congenital malformations and a 2-fold increase in the risk of pre-term births, relative to the reference-population prevalence.

Data Analysis

Demographic and baseline characteristics will be summarized with simple descriptive statistics and data listings for the evaluable population of pregnant women and live births.

Point estimates and 95% confidence intervals will be calculated using the binomial distribution for prevalence estimates of maternal death and pregnancy outcomes among pregnant women exposed to at least one dose of IV zanamivir and for birth outcomes including preterm birth, LBW, SGA and neonatal deaths among their exposed live births. Prevalence estimates for congenital malformations will consider congenital malformations identified in both live births and foetal deaths. For each prevalence estimate, both 1-sided and 2-sided 95% confidence intervals will be calculated and reported. Outcome prevalence estimates will be presented overall and stratified according to the trimester of IV zanamivir exposure.

The registry is primarily descriptive aiming to determine a signal for substantial increase in risk. Therefore, comparisons will be descriptive. Primary comparisons will be against external comparators reflecting population-based surveillance of pregnancy outcomes and literature-based disease cohorts. If it is feasible, descriptive comparisons between the registry and an appropriate internal comparator will be examined.

Milestones

The registry will be implemented following the granting of the marketing authorisation for IV zanamivir and before the start of the first northern hemisphere influenza season following that grant. The registry will be opened in countries within the European Union (EU), United Kingdom (UK), Norway and Iceland. At present 100-150 exposures during pregnancy to IV zanamivir are proposed to be sufficient to detect 2-4-fold increases in the risk of adverse pregnancy outcomes of interest and therefore sufficient to detect a signal for substantial increase in risk. The prevalence of exposure to IV zanamivir is likely to vary across influenza seasons influenced by factors such as the underlying pathogenicity and resistance profiles of circulating virus strains. Accordingly, an update report will be filed with the EMA each year, providing details of the number of treated patients enrolled and guidance on the likely study end date.

Amendment or update no.	Date	Section of study protocol	Amendment or update
1	23-JUN- 2020	8.4 Data source 8.7 Data Analysis, sub- section Analysis Population	Clarified that additional de-identified data, collected by HCPs to supplement the primary analysis population collected through the pregnancy study, can include the minimal dataset collected under informed consent waiver from the UKOSS/INOSS network. This will enable access to a minimal set of data on women exposed to IV zanamivir from UKOSS/INOSS but who do not consent to participate in the current study.

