8.5. Study size

The effect sizes that are expected to be detectable were calculated. The effect size is defined as the ratio of the prevalence in exposed patients, estimated from the study, to the prevalence in the reference population. These calculations were performed using a binomial distribution, a power of 80% and a 1-sided Type 1 (false positive) error rate of 5% [Altman, 1991]. Assuming prevalence values in the reference population of 2% (MCMs) and 7.6% (preterm births), 100 exposed live births will be sufficient to detect a 4-fold increase in the risk of MCMs and a 2-fold increase in the risk of pre-term birth, relative to the reference-population prevalence. The calculations were performed using the software PASS (Version 12.0.2, copyright 1983-2013, NCSS, LCC).

Table 1Detectable effect size assuming 80% power

Sample size of live births (N)	PTB reference 7.6% ¹	LBW reference 7.0% ¹	MCM reference 2.00% ²
5	6.45	7.00	24.51
20	4.12	3.69	10.10
50	2.61	2.83	5.38
100	2.05	2.07	3.90
150	1.85	1.91	2.99

Abbreviations: LBW = low birth weight; MCM = major congenital malformations; PTB = preterm birth. ¹Prevalence from Office for National Statistics, 2015 ²Prevalence from EUROCAT, 2017

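### 100 live births detect a 2.05-fold, not a 2-fold, rise in preterm birth at 80% power; power at exactly 2-fold is 77%

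*Protocol*

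**What the plan says.** The Study Size paragraph of the abstract describes calculations made "using a binomial distribution with 80% power and a 1-sided Type I (false positive) error rate of 5" per cent. With reference prevalences of 2% for major congenital malformations (MCMs) and 7.6% for preterm birth, it concludes that "100 exposed live births will be sufficient to detect a 4-fold increase in the risk of major congenital malformations and a 2-fold increase" in preterm birth.

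Section 8.5 repeats the conclusion in nearly the same words: "100 exposed live births will be sufficient to detect a 4-fold increase in the risk of MCMs and a 2-fold increase" in preterm birth. It states the method ("These calculations were performed using a binomial distribution") and the operating characteristics ("a power of 80% and a 1-sided Type 1 (false positive) error rate of 5" per cent).

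Table 1 follows in 8.5 and lists detectable ratios at 80% power. Its row for 100 live births reads 2.05 for preterm birth, 2.07 for low birth weight and 3.90 for MCMs.

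**The concern.** The sentence and the table rest on the same inputs, yet disagree on preterm birth. If the smallest ratio detectable with 80% power at 100 live births is 2.05, a ratio of 2.00 is detected with less than 80% power.

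Rounding a detectable ratio is harmless when it goes up and flattering when it goes down. In this sentence 3.90 became 4-fold for MCMs, which is safe. For preterm birth 2.05 became 2-fold, which overstates sensitivity. The abstract does not carry the table, so its reader cannot see the difference.

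What is at stake is how a null preterm result near 100 live births would be described: as having had 80% power against a doubling, when the power was somewhat lower.

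**Working it through.** **Inputs** (abstract, Study Size; section 8.5 and Table 1): reference prevalence p0 = 7.6% for preterm birth and 2% for MCMs; n = 100 live births; 1-sided error 5%; target power 80%; one-sample binomial comparison with a fixed reference.

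**Method.** The critical count r is the smallest count with P(X ≥ r | n, p0) ≤ 0.05. Power at ratio k is P(X ≥ r | n, k·p0). The detectable ratio is the k at which this power equals 0.80.

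**Step 1: reproduce Table 1.** This method returns all 15 cells to rounding. At n = 100:

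| Outcome | r | Actual error | Detectable ratio, recomputed | Table 1 |
|---|---|---|---|---|
| Preterm birth (7.6%) | 13 | 3.98% | 2.050 | 2.05 |
| Low birth weight (7.0%) | 12 | 4.69% | 2.071 | 2.07 |
| MCM (2%) | 6 | 1.55% | 3.896 | 3.90 |

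The table is therefore right, and the method is the one the protocol used.

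**Step 2: power at the ratio claimed for preterm birth.**
- Threshold: P(X ≥ 12 | 100, 0.076) = 0.0770, above 0.05. P(X ≥ 13 | 100, 0.076) = 0.0398, so r = 13.
- At 2-fold, p1 = 2 × 0.076 = 0.152: P(X ≥ 13 | 100, 0.152) = 0.7697, or 77.0%.
- At 2.05-fold, p1 = 2.05 × 0.076 = 0.1558: P(X ≥ 13) = 0.7997, or 80.0%.

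Shortfall at 2-fold: 80.0 − 77.0 = 3.0 percentage points.

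**Step 3: the MCM half of the sentence.** At 4-fold, p1 = 4 × 0.02 = 0.08: P(X ≥ 6 | 100, 0.08) = 0.8201, or 82.0%. This claim is met.

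**Step 4: could another formula support 2-fold at 100?** Power for 7.6% against 15.2% at n = 100:
- normal approximation, 1-sided, no continuity correction: 81.7%
- the same with continuity correction: 77.7%
- arcsine: 78.2%
- normal approximation, 2-sided 5%: 74.9%

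Only the uncorrected normal approximation reaches 80%. It gives a detectable ratio of 1.97, not the printed 2.05, so it is not the calculation behind Table 1.

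**Step 5: size needed for exactly 2-fold.** Exact power drops each time the critical count rises by one, so it does not climb steadily with n:

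| Live births | r | Power at 2-fold |
|---|---|---|
| 100 | 13 | 77.0% |
| 103 | 13 | 80.5% |
| 104 | 14 | 72.9% |
| 109 | 14 | 79.1% |
| 110 | 14 | 80.2% |
| 113 | 14 | 83.2% |
| 114 | 15 | 76.5% |
| 117 | 15 | 79.9% |
| 118 | 15 | 80.9% |

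From 100 upwards, power is at least 80% at 103, at 110 to 113, and at every size from 118 (checked to 399).

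**The case against.** The best defence is that this is rounding, disclosed on the spot. Section 8.5 speaks in whole folds and then prints 2.05 directly below, so a reader of that section has the exact figure. The gap is 3 power points, or three live births if one counts to the first size that reaches 80%. The registry is declared primarily descriptive and meant for signal detection, and results will be shown as prevalences with confidence intervals, so no pass/fail decision turns on 77% versus 80%. All of this stands, and it limits the weight of the point. It does not make the sentence correct: the protocol chose to state a power, an error rate and an effect size together, and the three do not fit.

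Some stronger readings are tempting but are not supported:

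- A reader might infer that 118 live births are required for a 2-fold rise. They are not: 103 and 110 to 113 also reach 80%. The size 118 is only where power stops dipping below 80%.
- A reader might extend the complaint to low birth weight, where power at 2-fold is 75.9% at 100. But neither the abstract nor 8.5 claims a 2-fold rise in low birth weight at 100 live births, and Table 1 reports 2.07 correctly.
- A reader might hold the broader statement that 100 to 150 exposures are "sufficient to detect 2-4-fold increases in the risk of adverse pregnancy outcomes of interest" to be wrong too. Taking the two ends of that range as live births, Table 1 runs from 2.05 to 3.90 at 100 and from 1.85 to 2.99 at 150. As a rounded summary across outcomes, 2 to 4 is fair.
- A reader might think the registry closes on the 2-fold figure. Section 8.9.1 fixes no closing size; annual updates to the EMA guide the end date.
- Table 1 lists five sizes and shows none of the dips between them. Each cell is correct at its own size and nothing is claimed for the sizes between, so this is ordinary presentation.

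**Conclusion.** The point holds in a narrow form. The statement in the abstract and 8.5 that 100 live births suffice for a 2-fold rise in preterm birth at 80% power is slightly optimistic. The protocol's own table gives 2.05, and exact power at 2-fold is 77.0%. The 4-fold MCM statement in the same sentence is correct, and so is Table 1.

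This rests on a reference of exactly 7.6%, a 1-sided 5% exact binomial test, and 100 evaluable live births in hand. It says nothing about how many exposures are needed to obtain them. The consequence is an overstated sensitivity of about 3 power points for one outcome. It does not affect the design, the analysis or the planned size.

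**What to change.** In the Study Size paragraph of the abstract and in 8.5, state that 100 live births detect a 2.05-fold (about 2.1-fold) increase in preterm birth with 80% power, and that power at exactly 2-fold is 77%. Leave the 4-fold MCM statement as it is.

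If a size for exactly 2-fold is wanted, say that power first reaches 80% at 103 live births and is at least 80% at every size from 118. Do not write that it is reached only from 118.

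Adding power figures for low birth weight, showing the minimum power over 100 to 150 live births, or rewording 8.9.1 is optional; none of these corrects an error.

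The cost is a few words in two places and a slightly less favourable stated sensitivity. No extra patients are needed.

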In the absence of appropriate influenza disease-based comparators these will form the primary population-based comparator groups.

Background Prevalence Estimates from Literature or Other Studies

The registry will identify other appropriate comparison groups through research of the literature and other sources, such as other pregnancy registries or observational studies. Particular attention will be paid to identify appropriate disease-based comparators in the literature, specifically pregnant women with influenza.

Concurrent comparator of untreated influenza pregnant women

Influenza itself is associated with adverse pregnancy outcomes and increased maternal influenza related mortality and morbidity. General population comparator groups will therefore not represent the same baseline risk of adverse pregnancy outcomes as women with influenza exposed to IV zanamivir. As treatment options may change over time, potential comparators will be assessed on a regular basis to assess if it will be feasible to enrol a disease comparator group that is unexposed to treatment or unexposed to IV zanamivir with similar underlying disease severity (complicated influenza).

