8.7.1. Essential analysis

This registry is primarily descriptive and designed to detect potential safety signals, rather than test hypotheses. GlaxoSmithKline is specifically interested in reporting the prevalence estimates of maternal deaths, birth outcomes and pregnancy outcomes including preterm birth, LBW, SGA and MCMs among pregnancies exposed to IV zanamivir and descriptively comparing them to external comparators to determine whether there is a signal of substantial increased risk with the IV zanamivir exposed group.

Demographic and baseline characteristics will be summarized with simple descriptive statistics and data listings for the evaluable populations of pregnant women and pregnancy outcomes. Demographic and baseline characteristics will also be summarized for the population that is lost to follow-up and compared with the evaluable populations to assess potential differences. These data will be reviewed for potential confounding factors that could affect the interpretation of comparisons of registry outcome prevalence estimates with those of comparators. Further details will be provided in the statistical analysis plan (SAP).

Prevalence point estimates and 95% confidence intervals will be calculated using the binomial distribution for prevalence estimates of maternal deaths, birth outcomes (live births, SAB, IABs, stillbirths) among pregnant women exposed to IV zanamivir and the pregnancy outcomes of preterm birth, LBW and SGA among their live births as well as MCMs among their live births and foetal deaths. For each prevalence estimate, both 1-sided and 2-sided 95% confidence intervals will be calculated and reported. One-sided confidence intervals are appropriate as we are specifically interested in detecting outcome prevalence estimates greater than their respective reference prevalence, and 2-sided confidence intervals will provide further description of the accuracy of the estimates. Prevalence estimates will be reported overall and according to the trimester of IV zanamivir exposure.

The prevalence of maternal deaths and birth outcomes (live births, SABs, IABs, stillbirths) will be calculated as proportions with the number of IV zanamivir exposed pregnancies as the denominator.

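### Table 1 and the intervals in 8.7.1 treat the reference prevalence as known, but literature disease cohorts are also primary comparators, and if small they need an interval that carries their own sampling error

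*Protocol*

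**What the plan says.** Protocol 8.5 sizes the registry as a single sample against a fixed number. It states: "These calculations were performed using a binomial distribution, a power of 80% and a 1-sided Type 1 (false positive) error rate of 5" per cent. On the effect measure: "The effect size is defined as the ratio of the prevalence in exposed patients, estimated from the study, to the prevalence in the reference population". The reference values are 7.6% for preterm birth and 7.0% for low birth weight (national statistics), and 2% for major congenital malformations (EUROCAT). Table 1 gives detectable ratios of "2.05 2.07 3.90" for 100 live births and "1.85 1.91 2.99" for 150, in the order preterm birth, low birth weight, malformations.

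Section 8.7.1 prescribes binomial intervals on each registry prevalence and explains the one-sided version: "One-sided confidence intervals are appropriate as we are specifically interested in detecting outcome prevalence estimates greater than their respective reference prevalence". It makes no provision for uncertainty in that reference.

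The comparators are broader than surveillance. The Abstract (Data Analysis) says: "Primary comparisons will be against external comparators reflecting population-based surveillance of pregnancy outcomes and literature-based disease cohorts". Section 8.2 (Reference Groups) also ranks published literature among the primary comparators. For malformations it makes EUROCAT and MACDP the fallback: "In the absence of appropriate influenza disease-based comparators these will form the primary population-based comparator groups". It leaves room for a concurrent group of women with complicated influenza not given IV zanamivir, if one can be recruited.

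**The concern.** A literature cohort or a concurrent group is a sample. Its observed prevalence can fall below its true value by chance, and a registry-only interval then makes the registry look raised when it is not. If the cohort is small, the comparison is a two-sample one, and neither the 5% error rate nor the 80% power behind Table 1 describes it.

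Section 8.2 accepts that general-population groups do not share the baseline risk of women with influenza. A disease cohort is therefore the comparison best placed to separate drug from disease, and it is the one whose sampling error the stated method leaves out.

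**Working it through.** **Inputs from the protocol.** One-sided 5%, 80% power, binomial; references 7.6% and 2%; N = 100 or 150 live births; ratios 2.05 and 3.90 at N = 100 (all 8.5). MACDP: 6,945 cases in 249,999 births, 2.78% (8.2).

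**Assumptions.** The comparator size M is not given, so a range is shown. No signal rule is given either. The rule examined is the natural reading of 8.7.1: a signal when the registry's one-sided 95% lower bound exceeds the comparator's observed prevalence.

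**Step 1: reproduce Table 1.** Find the smallest r with P(X ≥ r | N, p0) ≤ 0.05, solve P(X ≥ r | N, p1) = 0.80, and report p1/p0. At N = 100:

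| Outcome | r | Actual alpha | Ratio | Table 1 |
|---|---|---|---|---|
| Preterm birth, 7.6% | 13 | 3.98% | 2.05 | 2.05 |
| Low birth weight, 7.0% | 12 | 4.69% | 2.07 | 2.07 |
| Malformations, 2% | 6 | 1.55% | 3.90 | 3.90 |

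All 15 cells agree to rounding. Table 1 is a one-sample exact calculation with the reference known.

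**Step 2: how much comparator error is ignored.** The standard error is √(p(1−p)/M).
- MACDP: √(0.0278 × 0.9722 / 249,999) = 0.03 percentage points, which is negligible.
- A cohort of 100 at 7.6%: √(0.076 × 0.924 / 100) = 2.65 points, the same as the registry's own.
- A cohort of 250 at 7.6%: √(0.076 × 0.924 / 250) = 1.68 points.

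**Step 3: the rule against a finite cohort.** Let L(x) be the exact lower bound, the 5th percentile of Beta(x, N − x + 1), with L(0) = 0. Let Y be binomial (M, p0). Then

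P(signal) = Σx Bin(x; N, p1) × P(Y/M < L(x)).

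Setting p1 = p0 gives the false-signal rate; p1 = ratio × p0 gives power. Full enumeration gives:

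| M | Preterm, N = 100: false signal | Preterm, N = 100: power at 2.05 | Malformations, N = 100: false signal | Malformations, N = 100: power at 3.90 | Preterm, N = 150: false signal |
|---|---|---|---|---|---|
| 100 | 12.5% | 73% | 15.8% | 79% | 15.5% |
| 250 | 6.8% | 75% | 7.8% | 82% | 9.3% |
| 500 | 5.4% | 77% | 4.7% | 83% | 6.6% |
| 1,000 | 4.4% | 77% | 3.7% | 84% | 5.2% |
| Reference known | 4.0% | 80% | 1.5% | 80% | 3.6% |

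For preterm birth the false-signal rate is below 5% from about M = 650 at N = 100 (4.8%) and from about 1,100 at N = 150 (4.9%). For malformations it last exceeds 5% at about M = 525 (N = 100) and about 800 (N = 150). The figures do not move quite smoothly because the counts are discrete.

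**Step 4: a different baseline.** Section 6.1 cites a four-fold preterm risk in infected mothers. Taken as an assumption, 4 × 7.6% = 30.4%. At N = 100 the false-signal rate is then 11.7% (M = 100) and 7.3% (M = 250), much as before. The detectable ratio against a known reference of 30.4% is 1.40 rather than 2.05, so Table 1's ratios do not carry over to such a cohort even before its sampling error is counted.

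**The case against.** The strongest reply is that the protocol repeatedly calls the registry descriptive, says that it does not test hypotheses, and nowhere states that a lower bound above a comparator's point estimate is a signal. The detection claim in 8.5 is worded relative to the reference-population prevalence, with sources named. A disease cohort may never be found, and the form of interval for an unidentified comparator could be left to the SAP, which is not at hand.

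Much of this stands. The rule is inferred, the claim in 8.5 is already limited in scope, and surveillance comparisons are unaffected. It does not dispose of the point. The protocol itself fixes a registry-only interval, says what it is to be set against, and names disease cohorts as primary. The Abstract (Milestones) and 8.9.1 call 100–150 exposures sufficient without limiting that to surveillance references. A descriptive comparison of two samples still needs an interval that reflects both.

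A reader might infer two stronger things that the documents do not support:
- *That any finite comparator pushes false signals above 5%.* The exact rule has slack, and the excess fades above roughly 500–650 births at N = 100.
- *That the 80% power is lost in general.* A one-sided two-sample score test at the 2.05 ratio gives 55% (M = 100) and 71% (M = 250) for preterm birth, but the protocol does not use that test. Under its implied rule the loss is about 5–7 points for preterm birth, with almost none for malformations at N = 100.

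Nor can the inhaled-zanamivir studies in 6.1 (50 to 180 exposures) indicate the comparator's size: 8.2 rules out comparisons between inhaled and IV zanamivir.

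**Conclusion.** The point holds for small comparators. The sizing and the stated intervals suit EUROCAT, MACDP and national statistics. They do not suit a literature disease cohort or concurrent group of a few hundred births or fewer, although such cohorts are among the primary comparators. On the reading of 8.7.1 used here, the false-signal rate for preterm birth at N = 100 is about 12.5% with 100 comparator births and 6.8% with 250, against 4.0% for a known reference. Preterm-birth power falls from 80% to about 73–75%.

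These figures depend on an assumed comparator size, an inferred signal rule and equal true risk in the two groups for the false-signal rate. The point is moderate: worth correcting, but no threat to the surveillance comparisons.

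**What to change.** In 8.7.1, keep the one-sample binomial interval for comparisons with EUROCAT, MACDP and national statistics. For any literature cohort or concurrent group, report the prevalence ratio or difference with one-sided and two-sided 95% intervals computed from both numerators and both denominators, and base any signal statement on that interval.

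In 8.5, and where the Abstract (Milestones) and 8.9.1 call 100–150 exposures sufficient, state that the detectable ratios apply only to a reference prevalence treated as known at the tabulated values. Add that they do not carry over to a small disease cohort or to one with a different baseline.

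The cost is a few sentences and a routine calculation from published counts. Intervals against disease cohorts will be wider, and the sensitivity claimed for that comparison less favourable. No extra patients are needed.
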